Thus, current evidence suggests that weight loss programs that encourage moderate caloric restriction and increased physical activity may improve neural responses to food cues. Furthermore, decreased neural reward responsiveness to high-calorie food cues and increased responsiveness to low-calorie food cues may underlie improvements seen in self-reported and behavioral measures of appetite. Behavioral weight loss studies also suggest that weight loss induced through diet, physical activity, and lifestyle changes can improve brain structures and function associated with memory. However, this literature is limited by small sample sizes and the lack of randomized trials that have directly assessed these questions. The present study is significant because it will help to improve our understanding of neuronal correlates of weight loss interventions. A better understanding of brain mechanisms underlying weight loss can improve the efficacy of obesity prevention and treatment interventions.

2 Study Objectives

The purpose of the present study is to conduct a randomized controlled trial (RCT) to assess the effects of a commercially available weight loss program (WW; formerly Weight Watchers) on neural response to food cues and memory tasks, as well as on structural brain morphology. Participants with obesity will be randomized to either 16 weeks of a group-based WW program (n=30) or a wait-list control (WLC; n=30). Both groups will have structural and blood oxygen level-dependent (BOLD) functional magnetic resonance imaging (fMRI) scans at baseline and after the end of the intervention. Participants will complete the following fMRI tasks: 1) structural scans; 2) food cue task to measure reactivity to high and low-calorie food images;¹⁰ and 3) N-back task to measure working memory (i.e., the ability to temporarily hold information available for processing).⁵⁴ In addition, participants will complete self-report and behavioral measures of eating behaviors, appetite, physical activity, mood, quality of life, attention and memory at baseline, and weeks 8 and 16 (and at the end of the intervention).

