2.1 Primary Objectives

Aim 1: To compare differences between the WW and WLC groups at the end of the intervention in changes in BOLD fMRI response to food cues.

Hypothesis 1: We hypothesize that compared to the WLC, the WW group will have significantly greater declines in BOLD response to high-calorie foods in the reward regions of the brain (insula, orbitofrontal cortex, anterior cingulate cortex, nucleus accumbens) and significantly greater increases in BOLD response to low-calorie foods in these reward regions.

Aim 2a: To compare differences between the WW and WLC groups at the end of the intervention in changes in self-reported and behavioral measures of appetite, and **Aim 2b:** to test whether changes in self-reported and behavioral measures of appetite are associated with changes in neural responsivity to high and low-calorie foods in each study arm.

Hypothesis 2a: We hypothesize that at the end of the intervention the WW group, compared to the WLC group, will have significantly greater declines in self-reported reward-based eating, food cravings, hunger, and preference for high-calorie foods, and significantly greater increases in fullness after meals and preference for low-calorie food. *Hypothesis 2b:* We hypothesize that in the WW group, greater declines in BOLD responses to high-calorie foods will be associated with decreased (self-reported) wanting, liking, preference and craving of these foods, and that greater increases in BOLD response to low-calorie foods will be associated with increased wanting, liking, preference, and craving of low-calorie foods.

CONFIDENTIAL

This material is the property of the University of Pennsylvania.

Aim 3: To evaluate whether WW, compared to WLC, increases hippocampal volume from baseline to the end of the intervention.

Hypothesis 3: We hypothesize that compared to the WLC, WW will be associated with a significantly greater increase in the size of the hippocampus.

Aim 4: To compare differences between the WW and WLC groups at the end of the intervention in changes in BOLD fMRI response to the N-back task.⁵⁴

Hypothesis 4: We hypothesize that during the working memory task, the WW group, relative to the WLC group, will have significantly greater increases in BOLD activation in the hippocampus, dorsolateral and midventrolateral prefrontal cortex, posterior parietal cortex, and premotor cortex.

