After participants complete the screening procedures, provide their informed consent to participate, and are enrolled into the study, they will complete two study assessment visits that include fMRIs (one at baseline and one after 16-weeks) as well as a mid-point assessment at week 8 (that does not include an fMRI).

6.3 FMRI Assessments.

Prior to randomization, participants will complete a baseline fMRI assessment that will occur up to 4 weeks before the intervention begins. They will complete another fMRI assessment between 2 weeks before the end of the intervention (or up to 1 week after the study intervention is completed). The timeframe for the follow-up assessment was selected so participants in the WW group will be actively engaged in weight loss efforts at the time of the second scanning. Participants will be compensated \$100 for each fMRI assessment visit.

Planning for the Assessment Visit. Study assessment visits will be scheduled for the morning and last approximately 3 hours (60 minutes in the fMRI scanner and 120 minutes to complete questionnaires, behavioral tasks, and physical measurements). The visits will be held at the Hospital of the University of Pennsylvania. Participants will be asked to fast (including no caffeine or alcohol) for at least 8 hours prior to the appointment to increase the stimulus salience⁴¹ and create a more homogeneous hunger state across participants. Participants will be asked to remove all jewelry and metal objects at the visit. Participants who require vision correction will be instructed to wear contact lenses or will be provided with MRsafe glasses in their prescription strength.

Imaging Procedures

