6.6 Randomization Visit

Participants who meet all eligibility criteria assessed at the screening visit will be scheduled for a baseline fMRI assessment. The visit will occur within approximately 4 weeks of beginning treatment. They will be instructed to complete the self-reported outcomes either online (using a link e-mailed to them) or using paper-and-pencil questionnaires (for those who prefer this method) approximately 10 days before their fMRI scan. Their questionnaires will be reviewed for completeness at the fMRI visit, with any omissions or errors corrected. The randomization visit will include a weight, waist circumference, blood pressure, and heart rate, and completion of additional baseline assessments (as described in Table 2). Participants will then be randomly assigned to the two groups in equal numbers (i.e., 1:1 ratio). This will be accomplished using a computer-generated algorithm operated by faculty at the Center for Weight and Eating Disorders at the University of Pennsylvania (e.g., [name]). Assignment will be made from randomly varied block sizes (2 or 4). This is an open-labelled randomized trial. Due to COVID-19, we have combined the randomization visit with the baseline fMRI visit. After they complete their fMRI visit, they will be randomized to a treatment group.

CONFIDENTIAL

This material is the property of the University of Pennsylvania.

Table 1. Schedule of Study Assessments and Treatment Visits

	Weeks																																	
	8	9	10	11	12	13	14	15	16	17	18	19	20	21	22	23	24	25	26	27	28	29	30	31	32	33	34							
Screening																																		
FMRI Assessment																																		
Cognitive, Behavioral, and Self-report Assessments																																		
Randomization Visit																																		
WW Group Treatment																																		
WLC Group Treatment																																		

*WLC group only. For participants affected by COVID-19 and subsequent mandates necessary to help mitigate the transmission of the virus (e.g., stay-at-home orders), their fMRI assessments will occur at the end of the intervention. They will have questionnaire assessments administered at week 16 and then again at the end of the intervention when they can have their fMRI scan. The randomization visit will now be combined with the fMRI visit.

Table 2. Schedule of Procedures

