## Food Cues

Descriptive statistics summarized baseline and demographic characteristics. Baseline differences in BOLD response between stimuli classes (e.g., food vs. nonfood images and HCF vs. LCF) were examined using paired t-tests. Baseline differences between treatment groups' BOLD responses to image classes were examined using independent-sample t-tests. Statistical significance for baseline differences was  $p < .05$ . We tested changes in each ROI using general linear mixed models with repeated effects with the time variables (baseline vs. follow-up), group (BWL vs. WLC), and their interaction. Trial contrasts were assessed using the subtraction method (i.e., HCF minus neutral stimuli; LCF minus neutral stimuli). We also performed analyses with the individual stimulus type (i.e., HCF alone, LCF alone). Changes in self-report and behavioral variables were examined using general linear mixed models with repeated effects. We examined differences among groups in brain behavior relationships using correlations between BOLD activation changes in the ROIs and changes in self-report measures. For the primary analyses, p-values were adjusted for multiple testing of the ROIs using the Dubey/Armitage-Parmar Bonferroni method (Sankoh et al., 1997), as implemented in the Simple Interactive Statistical Analysis online calculator (<https://www.quantatitativeskills.com/sisa/calculations/bonfer.php?>; Alpha = 0.05 & N = 08 & Corr = 0.40 & Df = 00). Based on this calculation, primary outcomes' significance level was  $p = .01$ . Statistical significance was defined as  $p = .05$  for secondary exploratory outcomes.

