## Hippocampal Volume

Baseline and demographic characteristics were summarized by standard descriptive statistics. Neurocognition scores were converted to fully-demographically corrected T-scores. These scores have a mean of 50 and an SD of 10 and compare the score of the test-taker to those in the NIH Toolbox nationally representative normative sample, while adjusting for key demographic variables collected during the NIH Toolbox national norming study. Fully corrected T-scores represent an individual's level of cognitive functioning compared to age-, education-, sex-, and race/ethnicity-matched peers. Higher fully corrected T-scores indicate better performance. We tested change from baseline to follow-up in hippocampal volume and neurocognition using linear mixed models with maximum likelihood. We also explored whether, within the BWL group, baseline or change in hippocampal volume and neurocognition were correlated with percent weight loss. Statistical significance was defined as  $p < 0.05$  for all outcomes.

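### The food-cue ROI model compares change scores and does not use the pre-randomisation scan as an adjuster, which is valid but usually costs precision at 30 per arm and p = .01

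*SAP*

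**What the plan says.** The SAP section Food Cues fits, for each ROI, "general linear mixed models with repeated effects with the time variables (baseline vs. follow-up), group (BWL vs. WLC), and their interaction" (BWL is the WW arm, WLC the wait-list arm). The group term leaves each arm its own baseline mean. No baseline covariate is listed. Baseline differences between the arms are tested separately by t-test, but nothing says that the result enters the ROI model. On the adjusted level, the section says: "Based on this calculation, primary outcomes' significance level was" p = .01.

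The protocol fixes the order of events. Section 6.3: "Prior to randomization, participants will complete a baseline fMRI assessment that will occur up to 4 weeks before the intervention begins". Section 6.6, after the COVID-19 change: "After they complete their fMRI visit, they will be randomized to a treatment group".

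Aim 1 in section 2.1 is "To compare differences between the WW and WLC groups at the end of the intervention in changes in BOLD fMRI response to food cues". The planned size in section 2 is a "group-based WW program (n=30) or a wait-list control (WLC; n=30"). Section 6.6 sets the allocation ratio at 1:1.

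**The concern.** When the baseline measurement precedes randomisation, any baseline difference between the arms is chance. A model with free baseline means at two time points subtracts that chance difference in full, as if the slope of follow-up on baseline were 1. If the true slope is below 1, this adds noise to the treatment estimate. Baseline adjustment estimates the slope and targets the same between-arm difference.

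Precision matters here because the primary ROI tests have about 30 participants per arm and a .01 level. Only large effects can be detected, and a null result could reflect the choice of estimator as much as the biology.

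**Working it through.** **Inputs.** n = 30 per arm (Protocol 2, planned; the analysed number is not given). Significance level .01 (SAP, Food Cues), taken as two-sided because sidedness is not stated. Not in the documents and therefore assumed: ρ, the correlation between baseline and follow-up, from 0.3 to 0.9; k, the follow-up SD divided by the baseline SD, at 0.8, 1 and 1.25; a true effect of 0.8 follow-up SD; both scans present for everyone. The 0.40 in the SAP belongs to the adjustment for testing several ROIs and is not ρ.

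**The plan's own figure.** With 8 tests and correlation 0.40, the Dubey/Armitage-Parmar level is 1 − (1 − 0.05)^(1/8^0.6). Since 8^0.6 = 3.482, this is 0.0146. The stated .01 agrees to two decimals, and the rounding is conservative. I use .01. At 0.0146 and ρ = 0.5 the power contrast (normal approximation) is 0.74 against 0.87, so nothing below turns on the rounding.

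**Step 1: what the model estimates.** With two scans per person, the interaction is (follow-up minus baseline) in one arm less the same in the other. In a simulated data set the fitted mixed model gave 0.598 (SE 0.2692), and the difference in mean change was also 0.598 (SE 0.2692).

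**Step 2: variances.** Take the baseline SD as 1. The per-person variances, each multiplied by 2/n for the arm difference, are:
- change score: 1 + k² − 2ρk
- baseline-adjusted: k²(1 − ρ²), times 1 + 1/(60 − 4) = 1.018 for estimating the slope

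Before the slope cost, the first less the second is (1 − kρ)². Adjustment therefore never loses in large samples, and it gains nothing when the slope kρ equals 1. At k = 1 the ratio of adjusted to change-score variance is (1 + ρ)/2.

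**Step 3: equal SDs (k = 1).** Power and detectable effects use the noncentral t, with 58 df for the change score and 57 df for the adjusted analysis.

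| ρ | (1+ρ)/2 | ratio × 1.018 | 60 participants are worth | detectable at 80% power, change score | detectable at 80% power, adjusted |
|---|---|---|---|---|---|
| 0.3 | 0.65 | 0.66 | 91 | 1.075 SD | 0.875 SD |
| 0.5 | 0.75 | 0.76 | 79 | 0.909 SD | 0.794 SD |
| 0.7 | 0.85 | 0.87 | 69 | 0.704 SD | 0.655 SD |
| 0.9 | 0.95 | 0.97 | 62 | 0.406 SD | 0.400 SD |

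Power for a 0.8 SD effect, worked at ρ = 0.5:
- Change score: SE = √(2/30 × 1.00) = 0.258; 0.8/0.258 = 3.10; critical t = 2.663; power 67%.
- Adjusted: SE = √(2/30 × 0.763) = 0.226; 0.8/0.226 = 3.55; critical t = 2.665; power 81%.

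The same calculation gives 49% against 71% at ρ = 0.3, and 90.5% against 94.5% at ρ = 0.7. With equal SDs, the change score is at least as precise only when ρ exceeds about 0.965.

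**Step 4: unequal SDs.** The ratio is k²(1 − ρ²)/(1 + k² − 2ρk), times 1.018. At ρ = 0.3, 0.5, 0.7, 0.9:
- k = 0.8: 0.51, 0.58, 0.64, 0.62
- k = 1.25: 0.80, 0.91, 1.00, 0.97

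At k = 1.25 and ρ = 0.8 the slope kρ is exactly 1, and adjustment costs 1.8% in variance.

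**Step 5: simulation (40,000 trials per setting).** Empirical variance ratios at k = 1 were 0.66, 0.76, 0.87 and 0.97, matching Step 3. Type I error at .01 was 0.9% to 1.0% for both methods. With a true effect of 0.8 SD and ρ = 0.5, both estimators averaged 0.80, so they target the same quantity.

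**The case against.** The strongest defence is that the plan contains no error. The interaction is the literal estimator of an aim phrased as change, and it is unbiased and holds its level. That stands, and it is why this is a point of efficiency only. It does not favour the change score, because under randomisation the adjusted analysis estimates the same difference in change.

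A second objection is that the size of the loss cannot be read from the documents. That also stands: ρ, k and the 0.8 SD effect are assumptions. Protocol 5.4 lets the period before the final scan run from 16 to 36 weeks, which could widen the spread at follow-up (k above 1) and shrink the gain, though nothing shows that it did. The risk is still lopsided: adjustment costs about 2% in variance at worst, against a saving of about 34% at ρ = 0.3 with equal SDs.

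Third, the equivalence with a change-score comparison is exact only when both scans are present. If follow-up scans are missing, the planned likelihood model also draws on participants with a baseline scan only. The constrained model keeps those participants too; ANCOVA does not.

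Fourth, the SAP is written in the past tense, and replacing a primary model once results are known would be a post hoc change. That limits the form of the remedy.

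**Conclusion.** The point holds as a precision loss, not as a validity fault. The direction is well established. With equal SDs at the two scans, the planned ROI test gives up about 34%, 24%, 13% or 3% of the variance at correlations 0.3, 0.5, 0.7 and 0.9. The loss is larger if the follow-up SD is smaller than the baseline SD, and it can vanish if the follow-up SD is larger. These figures assume 30 per arm with both scans; the power figures also assume a two-sided .01 test. How much this trial loses depends on a correlation and an SD ratio that the documents do not report. It should be changed or supplemented, since the remedy uses data already collected, but the planned result remains interpretable without it.

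**What to change.** For the ROI outcomes, fit a constrained longitudinal model (one common baseline mean, time, and a group effect at follow-up only) by REML with small-sample degrees of freedom such as Kenward-Roger. ANCOVA of follow-up on baseline and group is an alternative, with a statement that it drops participants who have no follow-up scan.

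If results are already known, leave the planned analysis as primary. Report the adjusted analysis for every ROI beside it, labelled as a sensitivity analysis, so that neither can be picked for its result. In either case, report the observed baseline-to-follow-up correlation and both SDs for each ROI, so that readers can judge what adjustment was worth.

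The same form can serve hippocampal volume and the other outcomes, although the SAP lists no model terms there and the gain may be small. A minor side note on that section, which states: "We tested change from baseline to follow-up in hippocampal volume and neurocognition using linear mixed models with maximum likelihood". With 60 participants, maximum likelihood understates the SE by about 1.7% (√(58/60) = 0.983), which REML avoids.

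The cost is about one degree of freedom for the slope and, if the analysis is complete, a labelled re-analysis of the ROIs. No new data are needed.

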4.1 General Design

The proposed investigation is an open-label, RCT to assess changes in neural responses to food images and memory tasks in 60 participants with obesity who are randomized to a 16-week behavioral weight loss program (WW; n=30) versus a WLC group (n=30). Participants will be assessed at baseline and 16 weeks and at the end of the intervention, with the baseline and end of intervention assessments including structural and functional neuroimaging with BOLD fMRI. An additional assessment will occur at week 8 and include self-report measures only. Neither subjects nor investigators will be masked to treatment assignment.

CONFIDENTIAL

COVID-19 Changes. Due to the mandatory restrictions in research related to COVID-19, we have transitioned our in-person groups to group-based, remotely delivered sessions via Blue Jeans. We are also not able to conduct fMRI scans on participants and have extended weekly treatment for those people who are currently in the intervention arm (currently our first cohort of 10 participants). Extending treatment will help participants in the intervention arm continue to lose weight, which is an important mechanism we believe will be related to the fMRI results. The treatment will continue as it has, with remotely-delivered, group-based, behavioral weight loss sessions. Those on the wait-list have also had an extended time on the wait-list until we are able to conduct in-person, group treatment in accordance with University Guidance. We will administer the questionnaires at week 16 as in the original protocol. However, we will re-administer these questionnaires at the end of the intervention, once we are able to conduct fMRI scans on participants.

5 Study Population and Duration of Participation

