5.4 Duration of Study Participation

The maximum amount of time subjects in the WW group will participate in the study is 45 weeks (screening which may be up to 4 weeks before baseline fMRI; baseline fMRI which may occur up to 4 weeks before start of intervention; 16 to 36-week intervention; final fMRI up to 1-week post intervention period). The maximum amount of time the WLC subjects will participate in the study is 61 weeks (screening which may be up to 4 weeks before baseline fMRI; baseline fMRI which may occur up to 4 weeks before start of wait-list; 16 to 36 weeks on wait-list; final fMRI up to 1 week post wait-list period; 16 week intervention).

5.5 Vulnerable Populations:

Children, pregnant women, fetuses, neonates, or prisoners are not included in this research study.

6 Study Procedures

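### Scan-to-scan interval may run from 14 to 41 weeks, largely by COVID cohort, but the imaging models carry no cohort term: a modest precision loss and an estimate averaged over mixed exposure

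*SAP*

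**What the plan says.** **Model.** The SAP's Food Cues section fits "general linear mixed models with repeated effects with the time variables (baseline vs. follow-up), group (BWL vs. WLC), and their interaction". Time has two levels, whatever the number of weeks between scans. The Hippocampal Volume section describes linear mixed models for change from baseline to follow-up and lists no covariates. Neither section mentions cohort, scan interval or treatment length, or a sensitivity analysis on any of them.

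**Timing.** Protocol section 5.4 gives parallel windows for the two arms:
- WW: "baseline fMRI which may occur up to 4 weeks before start of intervention", then "16 to 36-week intervention; final fMRI up to 1-week post intervention period".
- Wait-list: "baseline fMRI which may occur up to 4 weeks before start of wait-list", then "16 to 36 weeks on wait-list; final fMRI up to 1 week post wait-list period".

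Section 6.3 places the second scan "between 2 weeks before the end of the intervention (or up to 1 week after the study intervention is completed".

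**COVID-19 changes.** Section 4.1 says that scanning was not possible, that weekly treatment was extended for a first intervention cohort of 10, and that groups moved to remote delivery. It expects the further weight loss to bear on the fMRI results. Wait-list participants had "extended time on the wait-list until we are able to conduct in-person, group treatment in accordance with University Guidance". Section 7 moves workshops after week 8 to video for the group then in treatment.

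**The concern.** Extended and non-extended participants differ in three things at once: length of treatment or waiting, mode of delivery, and calendar period. If change between scans depends on any of them, a model with only time, group and their interaction puts the cohort differences into the residual. That widens the standard error of the primary comparison in a trial of 30 per arm.

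There is also a question of meaning. The protocol presents a 16-week programme, but the group-by-time estimate averages over 16 weeks and anything up to 36. Because the protocol itself expects the extension to matter for the imaging result, a reader will want to know which duration the estimate describes.

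**Working it through.** **1. Check that the windows are read correctly.** Section 5.4 states maximum participation of 45 weeks (WW) and 61 weeks (wait-list).
- WW: 4 (screening) + 4 (baseline scan to start) + 36 + 1 = 45.
- Wait-list: 4 + 4 + 36 + 1 + 16 = 61.

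Both match.

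**2. Scan-to-scan interval** = (0 to 4) + (16 to 36) + (−2 to +1) weeks.
- Shortest: 0 + 16 − 2 = 14. The −2 comes from section 6.3; section 5.4 alone gives 16.
- Longest: 4 + 36 + 1 = 41.
- No extension: 14 to 4 + 16 + 1 = 21.
- Full extension: 36 − 2 = 34 to 41.

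The longest permitted interval is 41/14 = 2.9 times the shortest, and treatment length can differ by 36/16 = 2.25 times. The unextended and fully extended ranges do not overlap. These are permitted limits; the documents do not give the actual distribution.

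**3. Precision cost of omitting cohort.** The documents supplied give no SD, effect size, drift or number of cohorts, so these are assumptions. Take three cohorts of 20 (30 per arm in groups of 10), balanced by arm, a within-cohort SD of change of 1, and one cohort shifted by k SD in both arms. The between-cohort variance is h = (1/3)(2/3)k², and the standard error without the term is larger by √(1 + h) − 1.

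| k (SD) | h | Share of variance, h/(1+h) | SE larger by |
|---|---|---|---|
| 0 | 0 | 0% | 0% |
| 0.2 | 0.009 | 0.9% | 0.4% |
| 0.4 | 0.036 | 3.4% | 1.8% |
| 0.7 | 0.109 | 9.8% | 5.3% |
| 1.06 | 0.250 | 20% | 11.8% |

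The 0.2 to 0.4 SD rows correspond to a drift of 0.1 to 0.2 SD per 10 weeks over a 20-week extension. The lower rows need a much larger cohort difference.

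**4. Validity.** With arms balanced within cohort, the estimate itself is unaffected by a shift common to both arms; only its standard error is overstated. The true two-sided level is about 2[1 − Φ(z√(1 + h))].
- Nominal .05: 2[1 − Φ(1.96 × 1.053)] = .039 at k = 0.7, and 2[1 − Φ(1.96 × 1.118)] = .028 at k = 1.06.
- The SAP's primary .01: 2[1 − Φ(2.576 × 1.053)] = .007 and 2[1 − Φ(2.576 × 1.118)] = .004.

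The error is on the conservative side.

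**5. Mixed exposure.** Let d be the effect at 16 weeks, f the fraction extended, and r the ratio of the effect at the long interval to d. The single estimate targets d(1 − f + fr). With f = 1/3 assumed:
- r = 1 gives d.
- r = 1.5 gives 1.17d.
- r = 2.25 (effect proportional to weeks treated) gives 1.42d.

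If the effect grows with treatment, the average effect rises even though its duration is unclear. Cohort and cohort-by-time terms do not separate these exposures. That would need cohort-by-group-by-time terms or a restricted analysis.

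**The case against.** The strongest reply is that nothing is invalid. Assignment is 1:1 in blocks of 2 or 4 (section 6.6), so cohorts should be roughly balanced by arm and the unadjusted test is sound. At moderate drift the precision loss is under 2%. Averaging over programme length also fits the endpoint: sections 2.1 and 3.1.1 define the primary aims and endpoints at the end of the intervention, and section 7 describes workshops for 16 weeks or more. Appetite questionnaires were also given at week 16, so a 16-week comparison already exists for them. All of this stands, and it limits the point to efficiency and interpretation.

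A reader might go further and infer from section 4.1 that the second scan has a different trigger in each arm: scanner access for WW, the return of in-person groups for the wait-list. Drift would then be confounded with treatment. The documents do not support that as a finding. Section 5.4 gives both arms the same window. The notes to Tables 1 and 2 state one rule for COVID-affected participants, tied to when they can be scanned. Sections 6.5 and 7 offer WW to wait-list participants only after their second scan. The sentence in section 4.1 is best read as describing how long people waited for treatment. It is loose enough to permit an arm difference in interval, but it does not show one. Any bias figure would need an arm gap, an affected share and a drift rate, none of which the documents give.

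**Conclusion.** The concern holds as a modest one. The 14 to 41 week range follows from the protocol's own windows, tracks COVID cohort, and is not reflected in the imaging models. The cost is a standard error about 0.5 to 2% too large under moderate cohort shifts (0.2 to 0.4 SD), about 5 to 12% under large ones (0.7 to 1.06 SD), and zero if change does not differ by cohort. These figures rest on three balanced cohorts of 20 with one shifted, which the documents do not state. The primary test remains valid and slightly conservative.

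The interpretive point does not depend on those assumptions: without further reporting, the estimate cannot be tied to a 16-week programme. Bias from unequal intervals between arms is possible under the wording but not shown.

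**What to change.** 1. Add cohort and cohort-by-time as fixed effects to the region-of-interest, hippocampal and appetite models. Cohort is preferable to actual interval as the adjustment variable because it is fixed at entry, whereas the interval arises after randomisation. Cost: about 2 degrees of freedom with three cohorts, and no gain if cohorts do not differ.
2. Report weeks between scans by arm and cohort. This shows directly whether the arms differed.
3. Add one sensitivity analysis limited to participants scanned on the original 16-week schedule. This is the part that addresses mixed exposure. Cost: a smaller sample and wider intervals.
4. Reconcile section 4.1 on when the wait-list ends with sections 5.4, 6.3 and 6.6 and the notes to Tables 1 and 2, so that the timing of the second scan is stated identically for both arms. Sections 3.1.2, 6.2.2 and 13.1 still refer to week 16 and should be brought into line with the end-of-intervention wording used for the endpoints.

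No new data collection is needed provided that scan dates and cohort membership were kept. The SAP is written in the past tense; if the analyses have already been run, items 1 and 3 should be labelled as added afterwards and reported beside the planned model.
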